6.4.3 Subgroup Analyses

Modified DCR (Arms A & B combined) and ORR (arm C) will be summarized for following subgroups:

- Age (< 65, ≥ 65)
- Gender (Female and Male)
- Race (white, nonwhite)
- ECOG performance status (0, 1)
- Prior surgery status (biopsy only, partial resection, complete resection)
- Baseline corticosteroid use (yes, no)
- Methylation status (arm C only)

- Relapse status for arm C ORR only (first relapse, second relapse)

Forest plot will be provided for these subgroups as well. These planned subgroup analyses may not be explored if sufficient number of samples cannot be achieved for certain subgroups. The subgroup variables and the cutoff values are patient to change if warranted to better represent the data.

6.5 SAFETY ANALYSES

All safety analyses will be performed by dose cohorts (Phase 1b and Phase 2 will be presented as different table columns) and arms (A, B and C). Safety will be assessed by monitoring and recording of all AEs graded by CTCAE v4.03. Laboratory values (hematology, serum chemistry, coagulation, and urinalysis), vital signs, and ECGs findings will also be used in determining the safety. Descriptive statistics (n, mean, standard deviation, median, Q1, Q3, minimum, maximum for continuous variables; n [%] for categorical variables) will be used to analyze all safety data in the safety population.

6.5.1 Extent of Exposure

Descriptive summaries will be provided by cohort and each arms for following variables:

- Number of cycles received (in arm C and in Arms A and B for maintenance patients)
- Treatment duration (days) for all arms (see section 6.2.1 for definitions)
- Number of patients require dose interruptions and reductions
- Total dose received per patient (mg for pamiparib and TMZ, and Gy for RT)
- Dose intensity (mg/day for pamiparib and TMZ) and relative dose intensity. Dose intensity per patient is defined as sum of actual dose received divided by planned duration of treatment. Relative dose intensity is defined as total actual dose received divided by total planned dose. Total planned dose is the total dose that would be delivered, if there were no modification to dose or schedule.

Patients with dose reductions and interruptions and the reasons for reductions and interruptions will be listed.

6.5.2 Dose Limiting Toxicity

Dose-limiting toxicity in the DLT evaluation period will be assessed to determine the dose and schedule in phase 2. DLT events from the adverse event eCRF will be summarized descriptively for each dose cohort and arm in phase 1b in the DLT evaluable population.

6.5.3 Adverse Events

The AE verbatim descriptions (investigator terms from the eCRF) will be classified into standardized medical terminology using Medical Dictionary for Regulatory Activities (MedDRA). Adverse events will be coded to MedDRA (Version 22.0 or higher), lower level term closest to the verbatim term. The linked MedDRA preferred term (PT) and primary system organ class (SOC) are also captured in the database.

A treatment-emergent adverse event (TEAE) is defined as an AE that had an onset date on or after first dose of study treatment or was worsening in severity from baseline (pretreatment) up to 30 days following permanent study treatment discontinuation or initiation of new anti-cancer therapy, whichever occurs first. All AEs, treatment emergent or otherwise, will be presented in patient data listings. TEAEs will be summarized and presented for all cohorts and all arms.

An overview table, including the number and percentage of patients with any TEAEs, any treatment-related TEAEs, treatment-emergent serious adverse events (SAEs), TEAEs with grade 3 or above, treatment-related SAEs, TEAEs that led to death, and TEAEs that led to treatment discontinuation, dose reduction or dose interruption will be provided. Treatment-related AEs include those events considered by the investigator to be unlikely, possibly or probably or definitely related to study drug or with missing assessment of the causal relationship. The overview table will be completed for each study Arm.

The following TEAEs will also be tabulated in summary tables for all arms and cohorts:

- TEAE
- SAE
- TEAEs with grade 3 or above
- Treatment-related TEAEs
- Treatment-related SAEs
- TEAEs that led to death
- TEAEs leads to treatment discontinuation
- TEAEs leads to dose reduction or dose interruption of either Pamiparib or RT or TMZ

A patient will be counted only once by the highest severity grade according to CTCAE v.4.03 within an SOC and PT, even if the patient experienced more than 1 TEAE within a specific SOC and PT. TEAEs with grade 3 or above will also be summarized by PT in descending order.

In addition, the following listings will be provided:

- Listing of all AEs,
- Listing of all SAEs
- Treatment-related AEs
- Grade 3 or above AEs
- AEs leading to death
- AEs leading to treatment discontinuation

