7.1.4.2. Early Delayed

Possible early delayed radiation effects include lethargy and transient worsening of existing neurological deficits occurring 1-3 months after radiotherapy treatment.

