7.1.4.3. Late Delayed

Possible late delayed effects of radiotherapy, typically occurring >3 months after completion of RT, include radiation necrosis, endocrine dysfunction, and radiation-induced neoplasms. In addition, neurocognitive deficits, which could lead to mental slowing and behavioral change, are possible. Permanent hearing impairment and visual damage are rare. Cataracts can be encountered.

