10.3. Timing, Frequency, and Method of Capturing Adverse Events and Serious Adverse Events

10.3.1. Adverse Event Reporting Period

After the ICF has been signed but before study treatment, only SAEs should be reported, as required per [Section 10.5](#).

After initiation of study treatment, all AEs and SAEs, regardless of relationship to study treatment, will be reported until 30 days after the last study treatment or initiation of new anticancer therapy, whichever occurs first. After this period, the investigator should report any SAEs that are believed to be related to prior study treatment.

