- ^d For patients who have completed all study treatment per protocol and who do not continue on maintenance treatment with pamiparib in combination with TMZ, as described further below, the end-of-treatment (EOT) visit will occur at the end of the Rest Phase, 28 days after RT was completed. Patients who discontinued study treatment for any other reason outlined in [Section 6.5.1](#) will undergo the EOT visit within 7 days after stopping all study treatments. A visit should be scheduled as soon as possible, but the EOT visit may occur later after discussion with the medical monitor for specific circumstances, such as prolonged hospitalization. The visit at which MRI showed progressive disease (PD) may be used as the EOT visit provided that all required assessments were performed. MRI does not have to be repeated if it was performed within 14 days of the EOT visit or at a prior response evaluation that documented PD. ECG does not have to be repeated if it was performed within 14 days of the EOT visit.

After RT is completed, patients will receive no further RT. However, at the discretion of the investigator and after discussion with the medical monitor, patients may continue to receive pamiparib in combination with TMZ until PD, unacceptable toxicity or death, withdrawal of consent, loss to follow-up, or study termination by sponsor, as described in [Section 4.1.1](#) and [Section 4.1.2](#). This maintenance treatment should begin after the 4-week rest period post-completion of RT (+7 days) to allow for recovery from RT treatment. Patients should follow the Schedule of Assessments for the maintenance treatment ([Appendix 1 Table 4](#)).

- ^e Safety Follow-up: All patients who discontinue study treatment for reasons other than completion of RT per protocol will have a safety follow-up visit approximately

30 (± 7) days after the last day of study treatment to collect AEs and SAEs that may have occurred after the patient discontinued from the study treatment. For patients who have completed all study treatments per protocol, this safety follow-up coincides with the EOT visit.

Long-Term Follow-up: Patients who were not discontinued from study treatment due to PD and meet criteria otherwise (eg, discontinued for AE and no new anticancer therapy) will be followed every 8 weeks (± 7 days) until disease progression, administrative issues, start of other anticancer therapy or any other reason listed in [Section 6.7](#), whichever occurs first.

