6.2.2 Conventions

Unless otherwise specified, the following conventions will be applied to all analyses:

- 1 year = 365.25 days. Number of years is calculated as (days / 365.25) rounded up to 1 significant digit.
- 1 month = 30.4375 days. Number of months is calculated as (days / 30.4375) rounded up to 1 significant digit.
- Age will be calculated as the integer part of (first dose date – date of birth + 1)/365.25
- P-values will be rounded to 4 decimal places. P-values that round to 0.0000 will be presented as '< 0.0001' and p-values that round to 1.000 will be presented as '> 0.9999'.
- Duration of imaging-based event endpoints (such as PFS) will be based on the actual date the radiograph was obtained rather than the associated visit date.
- Missing efficacy or safety data will not be imputed unless otherwise specified.

- For by-visit observed data analyses, percentages will be calculated based on the number of patients with nonmissing data as the denominator, unless otherwise specified.
- For continuous endpoints, summary statistics will include n, mean, standard deviation, median, Q1, Q3 and range (minimum and maximum), unless otherwise specified.
- For discrete endpoints, summary statistics will include frequencies and percentages.

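### For Arm A and B patients without maintenance, related SAEs from delayed radiation effects fall after the 30-day TEAE window and reach listings but not the summary tables

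*SAP*

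**What the plan says.** SAP 6.5.3 (Adverse Events) ends the TEAE window "up to 30 days following permanent study treatment discontinuation or initiation of new anti-cancer therapy, whichever occurs first". It introduces the AE summary tables with "The following TEAEs will also be tabulated in summary tables for all arms and cohorts"; the items beneath include SAEs, treatment-related SAEs and events that led to death. AEs outside the window go into patient listings.

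Protocol 7.1.4.2 names lethargy and "transient worsening of existing neurological deficits occurring 1-3 months after radiotherapy treatment" as possible early delayed effects. Protocol 7.1.4.3 describes late effects as "typically occurring >3 months after completion of RT, include radiation necrosis, endocrine dysfunction, and radiation-induced neoplasms", and adds neurocognitive deficits.

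Protocol 10.3.1 collects all AEs until 30 days after the last study treatment, or until new anticancer therapy if that comes first. Then the rule narrows: "After this period, the investigator should report any SAEs that are believed to be related to prior study treatment". In Appendix Table 1, footnote e, "For patients who have completed all study treatments per protocol, this safety follow-up coincides with the EOT visit", and footnote d puts that visit 28 days after RT for patients who do not go on to maintenance.

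Maintenance with pamiparib plus TMZ is discretionary in both parts of Arm A and in Arm B escalation (protocol 4.1.1 and 4.1.2). It starts after a 4-week rest, with up to 7 further days allowed.

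**The concern.** Safety of pamiparib with RT is a primary Phase 1b objective in Arm A, and protocol 1.3.3 bases the combination on increased radiosensitivity of proliferating cells. Delayed neurological injury therefore matters for that objective, and the protocol itself says when to expect it. A safety table that closes before that period cannot show it.

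The window is also uneven. Maintenance keeps it open for weeks or months, so two patients with the same serious, related event on the same day after RT can be counted differently. Maintenance also requires patients to meet eligibility again at re-screening (Appendix Table 4, footnote a), so patients who deteriorate after RT may be the ones left with the short window. A reader who takes the SAE tables as complete for related events would be misled.

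**Working it through.** **Inputs.** RT lasts 6 to 7 weeks and Rest Day 1 is study day 43-50 (Appendix Table 1), so the last RT day is day 42 or 49. The TEAE cutoff is 30 days after the last study treatment (SAP 6.5.3). Delayed effects fall at 1-3 months and beyond 3 months (protocol 7.1.4.2 and 7.1.4.3). The SAP's convention is "1 month = 30.4375 days" (6.2.2). Maintenance starts 28 to 35 days after RT, in 28-day cycles (SAP 6.2.4).

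**Reproducing the schedule.** The EOT visit is Rest Day 29, which is the last RT day + 29: 42 + 29 = 71 and 49 + 29 = 78. This matches the stated day 71-78.

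**No maintenance (RT is the last study treatment).**
- The window closes at 42 + 30 = day 72, or 49 + 30 = day 79.
- The early delayed period starts at 42 + 30.4375 = day 72.4, or 49 + 30.4375 = day 79.4.
- It ends at 42 + 91.3125 = day 133.3, or 49 + 91.3125 = day 140.3.
- Overlap with the early period is 0%. It is also 0% with a 30-day month. With a 28-day month it is 30 − 28 = 2 of 56 days, or 3.6%.
- Overlap with the late period is 0 days in every variant.

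**With maintenance.** For k full cycles starting s days after RT, the window closes s + 28k + 30 days after RT. This assumes one continuous window from first dose through maintenance, and no new anticancer therapy, which would shorten it.

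| Course after RT | Window closes (days after RT) | Share of 1-3 month period covered | Days covered beyond 3 months |
|---|---|---|---|
| No maintenance | 30 | 0% | 0 |
| 1 cycle | 86-93 | 91-100% | 0-1.7 |
| 2 cycles | 114-121 | 100% | 22.7-29.7 |
| 4 cycles | 170-177 | 100% | 78.7-85.7 |

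Reaching 3 months after RT takes 91.3 − 30 − 35 = 26.3 to 91.3 − 30 − 28 = 33.3 days of maintenance. Late effects are thus only partly covered for anyone whose maintenance is short.

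**Example.** A serious, related neurological event occurs 2 months (60.9 days) after RT. After one maintenance cycle it falls before day 86-93 and is tabulated. Without maintenance it falls after day 30, is reportable under protocol 10.3.1, and goes to a listing only.

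**What is collected after day 30.** Without maintenance, only SAEs judged related to study treatment are required. During maintenance, all AEs are. Related SAEs are therefore the only class required in both groups.

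**A second clock.** Protocol 10.1.4 counts at least 30 days from the last pamiparib dose; 10.3.1 counts from the last study treatment. With 2 weeks of pamiparib, the first gives 14 + 30 = day 44, which is between 2 days after and 5 days before the end of RT. The two passages must be reconciled.

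**The case against.** The strongest reply is that the SAP does not settle what the tables contain. The overview table qualifies SAEs as treatment-emergent but lists treatment-related SAEs without that qualifier, and the list items for SAEs also omit it. Read literally, the TEAE sentence could even attach the 30-day limit only to events that worsen. This ambiguity is real. But the list is headed as TEAEs, and protocol 10.3.1 applies the 30 days to all AEs, so the natural programming leaves later events out. If the sponsor intends otherwise, one sentence would settle it.

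Several stronger readings are tempting, and the documents do not support them:
- *That brain toxicity in general is missing.* Acute toxicity, and anything with onset up to 30 days after RT, is tabulated.
- *That serious delayed injury goes unrecorded.* Related SAEs are reportable without a time limit, the adverse-event row of Appendix Table 1 extends into long-term follow-up, and all recorded AEs are listed.
- *That the choice of dose or schedule is distorted.* That rests on the DLT window (in Arm A, combination treatment plus 4 weeks; protocol 4.2.3 and SAP 6.5.2), not on the TEAE tables.
- *That the combination is made to look safer than an alternative.* The study is nonrandomised and the SAP plans no safety comparison. What can be said is that counts of related SAEs would be too low.
- *That a given share of patients is affected.* Any such share would be an assumption without a source.

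It is also fair to say that a 30-day window is common. Here, though, the protocol itself names a later risk period.

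**Conclusion.** The point holds in a limited form. Without maintenance, the TEAE window covers none of the early delayed period (at most 2 of 56 days on a 28-day month) and none of the late period. Related SAEs in those periods are collected but, on the natural reading of SAP 6.5.3, are not counted in any summary table. The same event in a patient on maintenance can be counted. For non-serious delayed events the gap lies in collection, and no table definition can repair it.

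The conclusion assumes that RT is the last study treatment for patients without maintenance, and that the SAE, related-SAE and fatal-event tables follow the TEAE heading. The number of uncounted events cannot be computed: no delayed-toxicity rate is given, and the number without maintenance could be anything from 0 to 40 of 40 in the Arm A expansion. Arm B contributes escalation patients only, because its expansion was not enrolled (SAP section 8). This is an inexpensive improvement to reporting on a primary Phase 1b safety objective; it does not show that the safety conclusions are wrong.

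**What to change.** - **SAP 6.5.3, tables.** State that the SAE, treatment-related SAE and fatal-event tables include treatment-related SAEs with onset at any time after first dose. Show those with onset more than 30 days after the last study treatment as a separate row, split by maintenance (yes/no) for Arms A and B.
- **Study report.** Say that non-serious delayed events after 30 days were not collected for patients without maintenance, so delayed-toxicity rates must not be compared or pooled across maintenance status.
- **No general interval table.** A table of RT-related neurological events by time since RT may look like the natural remedy. It would mix all-AE collection during maintenance with related-SAE-only collection without it, and so recreate the uneven counting. Use one only if it is restricted to related SAEs.
- **Protocol.** Reconcile the AE clocks in 10.1.4 and 10.3.1. AE collection could be extended at the existing 8-weekly visits, but the SAP already reports 116 patients enrolled, and this would help only those still in follow-up without progression or new therapy. After progression there is only contact about every 12 weeks for survival and further therapy.

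**Cost.** The table change uses data the protocol already requires. It needs minor programming and gives slightly higher SAE counts.

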1.2.4.1. Toxicity of Dose-dense Temozolomide Regimens

Studies have been conducted to assess the safety concerns (Neyns et al 2010). The greater dose intensity achieved in these studies does not appear to significantly increase the frequency of

thrombocytopenia or neutropenia (Gilbert et al 2013). Available data from Phase 2 trials indicate a high incidence of lymphopenia (8% to 68%), a common TMZ toxicity, and a slight increase in fatigue. Grade 3 or 4 lymphopenia in trials using the 21 of 28 days TMZ schedule (75 mg/m²) occurred in 24% to 53% of cases, and Grade 4 lymphopenia, which may increase the risk of opportunistic infections, was reported in 47% in one study for recurrent anaplastic astrocytoma or oligoastrocytoma (Neyns et al 2008).

In the RTOG 0525 study, adverse events (AEs) were evaluated separately during the concurrent chemo- and radiotherapy and the adjuvant treatment phase. Grade 3 or 4 lymphopenia was the most common toxicity occurring in 12% of patients but without significant opportunistic infections. Serious neutropenia and thrombocytopenia occurred in 3.6% and 6.8%, respectively, of all patients undergoing RT. There was one treatment-related death as a result of neutropenia (Gilbert et al 2013).

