3 STUDY OBJECTIVES

3.1 PRIMARY OBJECTIVES

3.1.1. Phase 1b

Arm A (pamiparib + RT): Patients with first-line unmethylated GBM

- To assess safety and tolerability of pamiparib combined with RT
- To identify dose-limiting toxicities (DLTs) and determine the maximum tolerated dose (MTD) or maximum administered dose (MAD) and length of treatment for pamiparib combined with RT
- To select the recommended Phase 2 schedule for pamiparib combined with RT

Arm B (pamiparib + RT + TMZ): Patients with first-line unmethylated GBM

- To assess safety and tolerability of pamiparib combined with RT and TMZ
- To identify DLTs and determine the MTD or MAD for TMZ when combined with RT and the length of pamiparib treatment in combination with RT as determined in arm A
- To select the recommended phase 2 dose (RP2D) for TMZ when combined with RT and the length of pamiparib treatment as determined in arm A

Arm C (pamiparib + TMZ): Patient with recurrent/refractory GBM

- To assess safety and tolerability of pamiparib combined with TMZ
- To identify DLTs and determine the MTD or MAD for TMZ combined with pamiparib
- To select the RP2D for TMZ combined with pamiparib

3.1.2 Phase 2

Arm A, Expansion (pamiparib + RT): Patients with first-line unmethylated GBM

- To make a preliminary assessment of efficacy of pamiparib combined with RT followed by maintenance treatment of pamiparib + TMZ for those patients continuing onto maintenance treatment

Arm C, Expansion (pamiparib + TMZ): Patients with recurrent/refractory unmethylated or methylated GBM

- To make a preliminary assessment of efficacy of pamiparib combined with TMZ

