6.2 DATA ANALYSIS GENERAL CONSIDERATIONS

6.2.1 Definitions and Computations

Study day: Study day will be calculated in reference to the first dose date of study drug. First dose date of study drug is defined as the earliest date of the first dose of any study drug. For maintenance phase, C1D1 is the first dose date. For assessments conducted on or after the first dose date, study day will be calculated as (assessment date – first dose date of study drug + 1). For assessments conducted before the first dose date, study day is calculated as (assessment date – first dose date of study drug). There is no study day 0.

In the situation where the event date is partial or missing, the date will appear partial or missing in the listings. Study day and any corresponding durations will be presented based on the imputations specified in [Appendix 1](#).

Baseline: Unless otherwise specified, a baseline value is defined as the last non-missing value collected before the time of first dose.

Treatment Duration:

Arm A&B regular treatment period (with RT) is defined as date of the last non-zero dose of latest treatment – first dose date of earliest treatment +1; treatment duration

Arm A&B maintenance period is defined as last non-zero dose of latest treatment in maintenance phase – date of C1D1 of maintenance phase +1

Arm C is defined as date of last non-zero dose of latest treatment – first dose date of earliest treatment +1.

RANO assessments:

ORR (objective response rate) is defined as proportion of patients with best overall response of CR or PR per RANO criteria (confirmed by a subsequent tumor assessment at least four weeks apart). Best overall response will be assessed from the start of study treatment until data cut-off date, disease progression or start of new anti-cancer therapy. Patients without postbaseline tumor assessment are considered non-responders.

Modified DCR (disease control rate) is defined as the proportion of patients with CR, PR or SD per RANO criteria as the response assessment at the end-of-treatment (EOT) visit, as

scheduled per protocol. Patients with no EOT tumor assessment, as scheduled per protocol (due to any reason), will be considered non-responders for modified DCR.

DCR (disease control rate) is defined as the proportion of patients with best overall response of CR, PR or SD per RANO criteria. CR or PR will be confirmed by a subsequent tumor assessment at least four weeks apart.

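### Arm A and B adverse-event and graded laboratory tables run RT and later pamiparib + TMZ maintenance together, so they do not isolate the tolerability of pamiparib + RT

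*SAP*

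**What the plan says.** SAP 6.5 sets the layout for all safety output: "All safety analyses will be performed by dose cohorts (Phase 1b and Phase 2 will be presented as different table columns) and arms". SAP 6.5.3 repeats it for adverse events: "TEAEs will be summarized and presented for all cohorts and all arms". An event is treatment-emergent if it starts or worsens after first dose, "up to 30 days following permanent study treatment discontinuation or initiation of new anti-cancer therapy, whichever occurs first". The counting rule is "A patient will be counted only once by the highest severity grade according to CTCAE v.4.03 within an SOC and PT". SAP 6.5.4 tabulates shifts from baseline to the maximum and last grade, and the worst grade, with no limit on postbaseline time. SAP 6.2.1 gives a single baseline, the last value before first dose.

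In Arms A and B, RT lasts 6 to 7 weeks. After a 4-week rest (+7 days), patients may receive pamiparib + TMZ in 28-day cycles (Protocol 4.1.1; SAP 6.2.4). In Arm A this is at the investigator's discretion after discussion with the medical monitor. Maintenance contains no RT and, for Arm A, introduces TMZ.

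The Phase 1b Arm A primary safety objective in SAP 3.1.1 is "To assess safety and tolerability of pamiparib combined with RT". SAP 4.1 makes adverse-event incidence and severity, and laboratory changes, Phase 1b primary endpoints.

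The SAP does recognise the two periods elsewhere. Under treatment duration in SAP 6.2.1, "Arm A&B maintenance period is defined as last non-zero dose of latest treatment in maintenance phase", counted from maintenance C1D1, with a separate formula for the RT period. The same section takes C1D1 as the first dose date for maintenance study days, and SAP 6.5.1 counts cycles for maintenance patients.

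**The concern.** A table meant to describe pamiparib + RT should not change with the number of patients who later receive another doublet, or with how long they stay on it. Under the present rules it does. An event that first appears, or first reaches its worst grade, during maintenance enters the same Arm A cell as an event during RT.

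The protocol gives reason to expect different toxicity. Section 1.2.4 says that low-dose TMZ given with RT rarely affects platelets or neutrophils, while the standard adjuvant schedule often does. Section 7.1.5.3 attributes Grade 3 or 4 events more to the added TMZ than to pamiparib alone. Section 1.2.4.1 notes that a cited randomized trial of dose-dense TMZ evaluated adverse events separately for the chemoradiation and adjuvant phases.

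At stake is whether the TEAE and graded laboratory results can be read against the stated Arm A objective.

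**Working it through.** The plan states no figure for this point, so the check is of definitions, followed by an illustration.

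**Timeline.** The Arm A DLT window is weeks of combination treatment + 4 (Protocol 4.2.3). For 2, 4 and 6 weeks of pamiparib this gives 2 + 4 = 6, 4 + 4 = 8 and 6 + 4 = 10 weeks, which matches the protocol's own 6- and 10-week examples. Scheduled maintenance starts after RT weeks + 4, up to one week later: from 6 + 4 = 10 to 7 + 4 + 1 = 12 weeks. On schedule, the DLT window closes before maintenance starts. The TEAE window does not close until after maintenance ends.

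**Which outputs mix the periods.**

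| Output | Time covered | Mixed? |
|---|---|---|
| TEAE tables (SAP 6.5.3) | First dose to end of TEAE window, once per patient at worst grade | Yes |
| Worst-grade and grade-shift laboratory tables (6.5.4) | All postbaseline time | Yes |
| By-visit laboratory and vital-sign summaries (6.5.4, 6.5.5) | Each visit | No |
| DLT summary (6.5.2) | DLT window, escalation cohorts only | No |
| Treatment duration (6.2.1) | Each period | No |

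**How much of the time can be maintenance.** Assume a patient stays on treatment to the unmethylated median PFS of 4.4 or 5.3 months, the two arms of the first Phase 3 trial in Protocol Table 1. With the SAP's month of 30.4375 days:
- 4.4 × 30.4375 / 7 = 19.1 weeks. A week-12 start leaves 19.1 − 12 = 7.1 weeks of maintenance (37%).
- 5.3 × 30.4375 / 7 = 23.0 weeks. A week-10 start leaves 23.0 − 10 = 13.0 weeks (57%).

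**Effect on a reported rate.** Let p1 be the share of patients with an event during RT or rest, p2 the share of maintenance patients with that event during maintenance, and f the share entering maintenance. If these are independent, the reported rate is 1 − (1 − p1)(1 − f × p2). All three inputs are assumptions. With p1 = 10%:

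| f | p2 = 10% | p2 = 20% | p2 = 30% |
|---|---|---|---|
| 25% | 12.25% | 14.50% | 16.75% |
| 50% | 14.50% | 19.00% | 23.50% |
| 75% | 16.75% | 23.50% | 30.25% |

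The lowest cell is 1 − 0.90 × (1 − 0.25 × 0.10) = 12.25%. The highest is 1 − 0.90 × (1 − 0.75 × 0.30) = 30.25%. A separate RT-period table would show 10% throughout.

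**The case against.** **Including maintenance is partly intended.** The Phase 1b primary endpoint on cycles and dose intensity names the Arm A and B maintenance phase (SAP 4.1), and the Phase 2 Arm A efficacy objective covers the sequence with maintenance (SAP 3.1.2). This stands: an overall table is a legitimate summary of what was given. It is a reason to keep that table, not a reason to have no other.

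**Timing can be recovered.** All adverse events are listed, and maintenance has its own study-day origin. This lowers the stakes, but a listing gives no incidence with a period-specific denominator. Relatedness does not separate the periods either, since SAP 6.5.3 counts even events judged unlikely to be related as treatment-related.

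**Splitting by onset can mislead.** Protocol 7.1.4.2 and 7.1.4.3 place early delayed RT effects 1 to 3 months after RT and late effects beyond that. Maintenance starts 4 to 5 weeks after RT, so for patients who continue, many such effects would leave the RT-period table. This objection stands in full and shapes the fix.

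Three stronger readings are tempting, and the documents do not support them:
- That Arm A has no safety result for pamiparib + RT. The DLT summary, treatment duration and by-visit summaries are unaffected.
- That the distortion can be sized from Protocol 1.2.4.1, where Grade 3 or 4 lymphopenia on TMZ 75 mg/m² for 21 of 28 days "occurred in 24% to 53% of cases". The share entering maintenance is not given, and the maintenance text states no TMZ dosing days. A patient already at that grade during RT would not be counted again.
- That the pooling spoils a comparison of Arm A with Arm B. No objective compares them, and the study is nonrandomized.

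**Conclusion.** The point holds for the TEAE, worst-grade laboratory and grade-shift tables, mainly in Arm A. As written, they cannot show the tolerability of pamiparib + RT on its own, although that is the Phase 1b Arm A primary safety objective. The same layout applies to the Arm A expansion column, where safety is a secondary endpoint (SAP 4.2) and there is no DLT summary to fall back on.

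The size is unknown, because the documents do not say how many patients entered maintenance. The 12% to 30% range for a 10% RT-period rate is an illustration that rests on the assumed rates, the assumed uptake and independence. If few patients continued, the effect is small, but the planned tables would not show which case applies.

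**What to change.** In SAP 6.5.3 and 6.5.4, add period-specific TEAE, worst-grade and grade-shift tables for Arms A and B, each with its own denominator:

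1. **RT + rest.** From first dose to the day before maintenance C1D1 for patients who continue. For those who do not, to the end of the existing TEAE window. A fixed 30-day cut-off after RT should not be used for patients who continue: maintenance can start up to 28 + 7 = 35 days after RT, so events from day 31 to C1D1 would fall in neither table.
2. **Maintenance.** From C1D1 to the end of the TEAE window, among patients who started maintenance. The baseline is the last value before C1D1, which the re-screening in Protocol Appendix Table 4 provides.

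Read the RT + rest table for the Phase 1b pamiparib + RT safety objective, alongside the retained overall table, which captures delayed RT effects that start during maintenance. State that link in the SAP.

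The cost is one period variable and a second set of tables. The remaining weakness is that delayed RT effects with onset in maintenance appear only in the maintenance and overall tables, so neither period table should be read alone.
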